5.3.11. Subgroup analysis

Subgroup analysis will be performed on the 4 groups including driver gene negative population, driver gene negative population (non-squamous cell carcinoma), driver gene positive population, and cohort 4 based on the following variables, which include: gender (male/female); age (≥ 65 years or < 65 years); ECOG performance status (0/1); smoking history (yes/no); number of metastasis sites (≤ 2 or > 2); clinical stage (stage IIIb/IV); brain metastases (yes/no); liver metastases (yes/no); history of tumor surgery (yes/no); history of radiotherapy (yes/no); PD-L1 expression levels on tumor cells (TC) in tumor tissues ($\geq 1\%$ / $< 1\%$); KRAS mutation (positive/negative), etc., and a forest plot of ORR (the vertical axis of Cohort 4 is 30%, and the vertical axis of other analyzed populations is 15%) will be drawn. In addition, subgroup analysis will be performed on the driver gene negative population, driver gene negative population (non-squamous cell carcinoma), and driver gene positive population based on the number of prior treatment lines (first-line/ \geq second-line). Subgroup analysis will also be performed on the driver gene positive population based on the gene mutation type (exon 19/L858R/exon 20).

Driver gene negative population (non-squamous cell carcinoma) refers to 1) Apatinib 250 mg + SHR1210 200 mg (Stage I): subjects who are negative or not tested for EGFR and also negative or not tested for ALK fusion gene; 2) Cohort 1: non-squamous, non-small cell lung cancer with wild-type EGFR and ALK.

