3 STUDY DESIGN

3.1 Overview of Study Design

Study design of Stage I:

A multi-arm, multi-center, open-label clinical study.

Inclusion criteria: Patients with advanced NSCLC who have failed standard treatment.

Three dose groups, i.e., 250 mg apatinib, oral, q.d. + 200 mg SHR-1210, IV, q2W, 375 mg apatinib, oral, q.d. + 200 mg SHR-1210, IV, q2W, and 500 mg apatinib, oral, q.d. + 200 mg SHR-1210, IV, q2W are set up. Ten to twelve subjects will be enrolled in each dose group (to make sure that at least 10 subjects will complete the tolerability evaluation), and the first cycle (28 days) of continuous treatment will be used as the observation period for tolerability. A dose will be considered tolerable if the proportion of subjects with clinically significant toxicity is < 0.33 .

Tolerability observation will be performed sequentially from the low dose group to the high dose group, and the tolerability observation of a latter dose group can only be carried out after the previous dose group is confirmed to be tolerable.

The first 3 subjects in each dose group will be enrolled on a case-by-case basis with an interval of not less than 14 days, and subsequent subjects can be enrolled at the same time.

After completing the tolerability observation period, subjects will continue the treatment until occurrence of any event that meets the criteria for discontinuation.

After the completion of the tolerability observation in Stage I, the study will enter Stage II for further observation of efficacy and safety.

In addition, after a certain dose group completes the tolerability observation in Stage I and is confirmed as tolerable, 10 to 12 subjects will be enrolled into this dose group for an expanded pharmacokinetic study. In cycle 1 of the expanded PK study, one dose of SHR-1210 will be administered on D1 followed by PK blood sampling. Then, apatinib will be started on D22 after the completion of PK blood sampling, while another PK blood sampling will be carried out on D28. Starting from D1 in cycle 2, SHR-1210 will be administered once every 14 days, while apatinib will be administered orally every day. PK blood sampling will be carried out on D1 of cycle 2 after the administration of SHR-1210 and on D28 after the administration of apatinib. After the blood sampling is completed, the subjects will continue to receive the study treatment until an event meeting the criteria of study termination occurs.

Design of Stage II Study:

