5 SUBJECT SELECTION AND WITHDRAWAL/DISCONTINUATION

5.1 Inclusion Criteria

Patients must meet all of the following criteria to be eligible for this study:

1. Male and female patients aged 18-70 years old;
2. Pathologically confirmed advanced (Phase IIIB and IV) non-small cell lung cancer with at least one measurable lesion that meets the RECIST v1.1 criteria and has not been treated locally;
3. Able to provide previous tumor samples or agree to cooperate with biopsy (Stage II);

4. Stage I: Patients who have undergone the second-line and above chemotherapy (at least one of the previous chemotherapy regimens is a platinum-based chemotherapy doublet regimen) but failed the treatment or showed recurrence. The patients harboring EGFR mutations and ALK gene abnormalities must have failed the treatment with an EGFR inhibitor or ALK inhibitor.

Stage II: Patients who have undergone only one previous platinum-based doublet chemotherapy but failed the treatment or showed recurrence, or patients in the stage of palliative treatment who have received no systemic treatment (only for cohort 4).

- a. The replacement of platinum drugs due to drug toxicity will be considered as one treatment regimen;
- b. Postoperative adjuvant chemotherapy will not be counted as one previous chemotherapy regimen if the time from the end of treatment to recurrence is > 6 months.

According to the type of driver gene mutations and pathological classification, the subjects will be divided into the following four cohorts:

Cohort 1. Patients with confirmed absence of mutations in EGFR 18-21 exons and ALK fusion genes (the histochemistry result of ALK D5F3 antibody is negative);

Cohort 2. Patients with confirmed presence of mutations in EGFR 18-21 exons or ALK fusion genes (the histochemistry result of ALK D5F3 antibody is positive). Carriers of sensitive EGFR mutations must have received at least one targeted treatment with EGFR tyrosine kinase inhibitors (EGFR-TKI) and failed the treatment. Carriers of positive ALK fusion genes must have failed the treatment of at least one targeted treatment with ALK tyrosine kinase inhibitor (ALK-TKI) (treatment failure: progressive disease or intolerable toxicity during the treatment);

Cohort 3. Imaging confirmed non-central squamous cell lung cancer or adenosquamous carcinoma primarily consisted of squamous cell carcinoma (pathologically confirmed).

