7.1 Screening Period (D-21 to D-1)

Unless otherwise stated, the following screening procedures must be completed within 21 days prior to the first dose:

[Signing of ICF] A written ICF must be signed by the subject before any procedures of the clinical study are carried out.

[Demographics] gender, date of birth, ethnicity, height, weight, smoking history.

[Tumor history] including pathological diagnosis and clinical diagnosis:

- (1) Tumor diagnosis: the date of initial diagnosis of the tumor, histological classification, site of primary tumor and metastatic lesions, pathological staging, and clinical staging;
- (2) History of surgery: the surgical history of primary lesions and the surgical history of metastatic lesions;
- (3) History of chemotherapy (including new/adjuvant chemotherapy): the history of systemic chemotherapy, the history of targeted drug therapy, and the history of local chemotherapy;
- (4) History of radiotherapy: date, dose, and site (systemic/local);
- (5) Results of gene mutation detection (if applicable): whether there are gene mutations, sites of mutation, and detection date;
- (6) The date of PD or disease recurrence after the last systemic treatment.

[Concomitant disease] Concomitant disease and related treatment history (such as diabetes, hypertension and other chronic diseases), history of tumors other than non-small cell lung cancer.

[Concomitant medication] Concomitant medications and treatments received within 30 days prior to the first dose and during the study period should be recorded. Once the study treatment is interrupted, only the concomitant medication and treatment used to solve new or unresolved treatment-related AEs will be recorded;

[Thyroid function] Including serum FT3, FT4, and TSH;

[Examination of the pituitary adrenal axis] Including ACTH and cortisol.

[Hepatitis B, hepatitis C, and HIV examinations] hepatitis B panel (If the test results are abnormal, viral replication [HBV DNA] test should be performed); hepatitis C virus antibody (anti-HCV) test (If the test results are abnormal, virus titer should be tested); HIV antibody test.

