5. STATISTICAL ANALYSIS

All efficacy and safety analyses will be based on the following populations/groups:

- **Driver gene negative population:** Subjects who are negative or not tested for EGFR and also negative or not tested for ALK fusion gene are classified into negative population. Including:
 - (1) Apatinib 250 mg + SHR1210 200 mg (Stage I): subjects who are negative or not tested for EGFR and also negative or not tested for ALK fusion gene;
 - (2) Cohort 1;
 - (3) Cohort 3;

Apatinib 250 mg + SHR1210 200 mg are used in both Cohorts 1 and 3 in Stage II.

- **Driver gene positive population:** Subjects who are positive for EGFR or ALK fusion gene are classified into positive population. Including:
 - Subjects who use apatinib 250 mg + SHR1210 200 mg and are positive for EGFR or ALK fusion gene in Stage I;
 - Cohort 2: Apatinib 250 mg + SHR1210 200 mg are used in Cohort 2.
- **Cohort 4:** Apatinib 250 mg + SHR1210 200 mg are used in Cohort 4.
- **Apatinib 375 mg + SHR1210 200 mg:** Only subjects who receive apatinib 375 mg + SHR1210 200 mg in Stage I are included.

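### The SAP's non-squamous driver-negative population has no histology condition on its Stage I part, so any squamous Stage I subject who meets its gene-status rule would be counted as non-squamous

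*SAP*

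**What the plan says.** SAP section 5 builds the full driver-negative population from three parts: a Stage I part, Cohort 1 and Cohort 3 (squamous). The Stage I part reads "1) Apatinib 250 mg + SHR1210 200 mg (Stage I): subjects who are negative or not tested for EGFR and also negative or" untested for ALK.

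SAP 5.3.10 (biomarker analyses) and 5.3.11 (subgroups) then introduce a narrower population meant to isolate non-squamous disease. Both sections use the same definition: "Driver gene negative population (non-squamous cell carcinoma) refers to 1) Apatinib 250 mg + SHR1210 200 mg (Stage I): subjects who are negative" or untested for EGFR, and likewise for ALK. Its second part is "2) Cohort 1: non-squamous, non-small cell lung cancer with wild-type EGFR and ALK". Histology is stated for Cohort 1 and not for Stage I.

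The protocol does not supply the missing limit. Section 3.1 gives the Stage I population as "Inclusion criteria: Patients with advanced NSCLC who have failed standard treatment". The disease criterion in section 5.1 is "Pathologically confirmed advanced (Phase IIIB and IV) non-small cell lung cancer with at least one measurable lesion", and the criterion specific to Stage I concerns earlier treatment: "Stage I: Patients who have undergone the second-line and above chemotherapy". No exclusion criterion in section 5.2 names squamous histology.

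**The concern.** The only purpose of the narrower population is to remove squamous disease. As defined, it removes Cohort 3 and nothing else; the Stage I part passes through unchanged. One programmer following the text and another following the label could build different populations, which an SAP is meant to prevent.

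This population carries its own ORR forest plot with a 15% reference line, a further subgroup analysis by number of prior treatment lines, and ORR, PFS and OS by biomarker level. If squamous subjects were present in the Stage I part, those estimates would be reported under a label that does not describe the subjects in them.

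**Working it through.** The plan states no size for this population, so the check is a comparison of definitions followed by a bound on the possible effect.

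**Definitions side by side**

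| Population | Stage I conditions | Histology condition on Stage I | Stage II part |
|---|---|---|---|
| Full driver-negative (SAP 5) | 250 mg dose; EGFR and ALK each negative or untested | none | Cohorts 1 and 3 |
| Non-squamous driver-negative (SAP 5.3.10, 5.3.11) | the same, word for word | none | Cohort 1 |

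The two differ only by Cohort 3.

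**Size of the Stage I part**

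- Protocol 3.1: 10 to 12 tolerability subjects plus 10 to 12 PK-expansion subjects per dose group, so 20 to 24.
- Protocol 3.1.2 lets a tolerability group close once 7 subjects are free of clinically significant toxicity, so the lower end is about 7 + 10 = 17.
- Cohort 1 (SAP 2.3): 62 / (1 − 0.20) = 77.5, rounded up to 78, which reproduces the plan's figure.
- Stage I share of the pooled group: 17 / (17 + 78) = 17/95 = 17.9%; 24 / (24 + 78) = 24/102 = 23.5%.

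These shares are maxima for the planned sizes, because they treat every Stage I 250 mg subject as negative or untested. Stage I also admits EGFR/ALK carriers, whom SAP section 5 places in the driver-positive population.

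**Possible number misfiled**

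The documents give no squamous share for Stage I. Assume 0% to 50%:

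- lowest: 0 subjects;
- highest: 24 × 0.50 = 12 subjects, or 12/102 = 11.8% of the pooled group.

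**Possible effect on the pooled ORR**

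Take a non-squamous ORR of 30% (the Cohort 1 planning value, SAP 2.3) and an assumed squamous ORR q of 0% to 45%. With k misfiled subjects in a total of T, pooled ORR = [0.30 × (T − k) + q × k] / T. At T = 102 and k = 12:

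- q = 0: (0.30 × 90) / 102 = 27.0/102 = 26.5%;
- q = 0.45: (27.0 + 5.4) / 102 = 31.8%.

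**The row with two or more prior lines**

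SAP 5.3.11 also splits this population by number of prior treatment lines. Stage I requires second-line or later chemotherapy, while Cohort 1 subjects are to have had a single platinum doublet. The higher-line row would therefore consist mainly of Stage I subjects, and Cohort 1 would not dilute an error there. For a row made up only of Stage I subjects with squamous share f, ORR = 0.30 × (1 − f) + q × f:

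- f = 0.20: 24.0% (q = 0) to 33.0% (q = 0.45);
- f = 0.50: 15.0% (q = 0) to 37.5% (q = 0.45).

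**Which biomarker splits are reached**

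Protocol 3.3 plans baseline blood for all enrolled subjects (bTMB and PD-L1 on circulating tumour cells) but baseline tissue for Stage II participants. Inclusion criterion 3 also ties the tissue requirement to Stage II. On that text, Stage I subjects have no planned tissue PD-L1, TAM or tissue TMB value and would not enter those splits. Note 28 to the schedule of activities does not repeat the Stage II limit, so this is not certain.

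**The case against.** The strongest reply is that no error may occur at all. A reader might infer from the missing filter that squamous patients are in fact analysed as non-squamous and that every result for this population is therefore mislabelled. The documents do not support that. They never say that a squamous, driver-negative or untested patient entered Stage I at 250 mg. The SAP's analysis groups omit the planned 500 mg group, which suggests they may have been drawn up with knowledge of who was enrolled. If there was no such patient, the definition gives the right population. Tissue-marker splits may also be untouched, for the reason above. This objection stands, and it makes the point conditional.

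A second reply is that the label itself implies a filter. This is weaker. The operative text follows the label, states histology for one part and omits it for the other, and does so in both sections.

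A third is that Protocol 5.2 criterion 6 excludes cavitated or necrotic lung tumours, with a possible exception only for marginal adenocarcinoma. That might reduce squamous enrolment, but it does not exclude squamous disease.

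A fourth is that little depends on this. SAP section 3 disclaims formal hypotheses, so the 15% line is a plotting reference and not a test. SAP 5.3 also presents efficacy by cohort. The extreme pooled shift above, 3.5 points, is well inside a normal-approximation 95% half-width of 1.96 × √(0.30 × 0.70 / 102) = 8.9 points. This limits the severity. It does not make the definition right, and it does not cover the higher-line row.

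**Conclusion.** The definition is wrong as written, with minor to moderate consequences confined to exploratory and subgroup analyses. Its Stage I part does not do what the label says: any squamous Stage I 250 mg subject who is negative or untested for both genes would be counted as non-squamous.

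The number of such subjects is unknown. On planned sizes it lies between 0 and 12 of at most 102, assuming a squamous share of 0% to 50% and no driver-positive subjects in Stage I at 250 mg. The pooled ORR would then stay within 26.5% to 31.8% around a true 30%, given an assumed squamous ORR of 0% to 45%. The row with two or more prior lines is the most exposed. The blood-marker splits of ORR, PFS and OS are also reached; the tissue-marker splits are reached only if Stage I tissue was collected. It would go too far to say that misclassification has happened, or that all of this population's results are affected.

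**What to change.** In both SAP 5.3.10 and 5.3.11, add a condition of non-squamous histology to part 1 of the definition and leave the dose and gene-status conditions as they are. State that adenosquamous tumours that are predominantly squamous count as squamous, in line with the Cohort 3 criterion in Protocol 5.1, and say how unknown histology is handled.

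No new data are needed: the protocol's screening procedures (section 7.1) already record "histological classification, site of primary tumor and metastatic lesions", and SAP 5.2.3 summarises and lists it. The cost is a few words in two places and one filter in the program. SAP section 2 provides for the plan to be finalised before database lock, so the change belongs before that step.

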5.3.12. Other analyses

NA.

5.4. Safety Analysis

All safety analyses will be conducted based on the SS.

5.4.1. Extent of exposure

Extent of exposure is defined in Section 5.1.3. The specific definitions of the derived variables of apatinib and SHR1210 are shown in [Table 2](#) and [Table 3](#).

The actual cumulative dose of all cycles, duration of drug exposure, actual dose intensity, relative dose intensity, etc. of apatinib, and the actual cumulative doses of all cycles, duration of drug exposure, actual dose frequency intensity, and relative dose frequency intensity of SHR1210 will all be described using mean, standard deviation, maximum, minimum, and median. The use of study drugs SHR-1210 and apatinib in the treatment period will be summarized by descriptive statistics. For the relative dose frequency intensity of SHR-1210, the relative dose intensity values of apatinib are summarized in two categories: $<$ or $\geq 80\%$.

The dose interruption and dose modification of apatinib and the dose interruption of SHR1210 during the study will be summarized.

5.4.2. DLT evaluation

DLT analysis is based on DLT analysis set. Clinically significant toxicity events will be listed. Clinically significant toxicities will be summarized by dose group using frequency and percentage.

5.4.3. Adverse events

AEs will be classified by treatment stage (before and after study treatment).

All AEs will be coded using MedDRA V24.0 and graded using NCI-CTCAE v4.03. Subject will be counted only once, even if the subject experiences more than one event within the same system organ class (SOC) and/or preferred term (PT). For the same AE reported in one subject multiple times but varying in CTCAE grade, the highest grade will be counted.

AEs will be ordered by descending incidence of SOC, and by descending incidence of PT within each SOC. If the incidence of ≥ 2 PTs is equal, the AEs will be ordered alphabetically. If there is no AE under a SOC or PT, the analysis will not be conducted.

Only TEAEs will be summarized. All AEs will be listed. AEs with completely missing onset time will be treated as TEAEs.

For AEs occurring after the start of study treatment, treatment-related AEs include those whose causality with the study drug is related, possibly related, or unassessable; if the causality assessment is missing, then the AE will be deemed treatment-related for analysis. AEs with any missing CTCAE grade will be analyzed based on the highest grade.

In AE summary table, AEs after study drug treatment will be analyzed according to the population/cohort, and the frequency and proportion will be used for statistical description. Analyses of AEs include but are not limited to the following:

- Any TEAE
- Treatment-related TEAE
- Any treatment-emergent serious adverse event (TESAE)
- Treatment-related TESAE
- CTCAE Grade ≥ 3 TEAE
- CTCAE Grade ≥ 3 treatment-related TEAEs
- Any TEAE with an incidence of $\geq 5\%$
- Treatment-related TEAE with an incidence of $\geq 5\%$
- AEs leading to treatment discontinuation
- Treatment-related AEs leading to treatment discontinuation
- AEs leading to discontinuation of SHR-1210
- Treatment-related AEs leading to discontinuation of SHR-1210
- AEs leading to discontinuation of apatinib
- Treatment-related AEs leading to discontinuation of apatinib
- AEs leading to interruption of SHR-1210
- Treatment-related AEs leading to interruption of SHR-1210
- AEs leading to interruption of apatinib
- Treatment-related AEs leading to interruption of apatinib
- AEs leading to dose reduction of apatinib
- Treatment-related AEs leading to dose reduction of apatinib
- AEs leading to death
- Treatment-related AEs leading to death
- TEAEs of special interest (SIEs, see Appendix 2 for specific classification)
- Immune-related TEAEs (irAEs)

The incidence of an AE will be calculated based on the number of subjects experiencing the AE, instead of the number of AE episodes.

SIEs include:

- Grade ≥ 3 infusion reaction
- Grade ≥ 2 diarrhea/colitis, uveitis, and interstitial pneumonia
- Other Grade ≥ 3 irAEs
- Grade 4 amylase or lipase increased
- Reactive capillary endothelial proliferation
- Hepatic enzyme abnormal

Time to the first onset of event (days) = Date of first onset of event – Date of first dose + 1;

All AEs will be listed. Treatment-related AEs, SAEs, irAEs, and AEs leading to treatment discontinuation, interruption, or dose reduction will be listed separately.

In addition, AEs will be summarized by group (apatinib 250 mg + SHR1210 200 mg, apatinib 375 mg + SHR1210 200 mg) using descriptive statistics, including but not limited to the following:

- Any TEAE
- Treatment-related TEAE
- Any treatment-emergent serious adverse event (TESAE)
- Treatment-related TESAE
- CTCAE Grade ≥ 3 TEAE
- CTCAE Grade ≥ 3 treatment-related AEs
- Special interest events (SIEs)
- Immune-related adverse events (irAEs)
- Treatment-related AEs leading to treatment discontinuation
- Treatment-related AEs leading to discontinuation of SHR-1210
- Treatment-related AEs leading to discontinuation of apatinib
- Treatment-related AEs leading to interruption of SHR-1210
- Treatment-related AEs leading to interruption of apatinib
- Treatment-related AEs leading to dose reduction of apatinib

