CYP3A4 substrates prohibited during the study (drugs with narrow safety windows and may cause serious adverse reactions when their metabolism is affected) include but are not limited to:

- Hypoglycemic agents: tolbutamide, chlorpropamide
- Ergot derivatives: dihydroergotamine, ergometrine, ergotamine, methyl ergometrine (potential risk of ergot poisoning, including severe vasospasm leading to peripheral and cerebral ischemia)
- Antipsychotic: pimozide (can potentially increase the risk of prolonged QT interval)
- Antiarrhythmics: amiodarone (prohibited within 6 months prior to randomization), bepridil, flecainide, lidocaine, mexiletine, quinidine, and propafenone
- Immunomodulators: cyclosporine, tacrolimus, sirolimus (may potentially increase the risk of nephrotoxicity and neurotoxicity)
- Miscellaneous: quetiapine, risperidone, clozapine, tomoxetine hydrochloride

If warfarin is used for anticoagulation during the study, a reduced dose should be considered with its use being monitored closely, and the use of the study drugs should be discontinued if necessary.

During the treatment period, anti-tumor drugs and adjuvant drugs related to tumor treatment, such as anti-tumor traditional Chinese medicine (see Appendix I for a detailed list), immunological agents, etc., should be discontinued.

6.6.2 Drugs and treatments that may be used as appropriate during the study:

In Stage I, for subjects enrolled in the tolerability observation study, except that the subjects experiencing hypertension, rash, diarrhea, nausea and vomiting can be given symptomatic treatments, all other adverse reactions with no clinically significant toxicity occurring during the tolerability observation period (Cycle 1 of drug administration) will not be treated in principle, so as to observe the possible adverse effects and their extent/reversibility of the study drugs. However, in the event of a clinically significant toxicity as specified in the protocol, the treatment should be interrupted and a proactive approach should be used to manage the event. Used medications should be recorded on the eCRF. For subjects experiencing clinically significant toxicity, the treatment can be resumed at the original dose (when the original dose is the lowest dose) or the nearest lower level after the toxicity returns to Grade ≤ 1 after management.

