In other cases, the subjects should be given an optimal supportive care during the treatment. Comorbidities and various adverse reactions, especially immune-related adverse reactions, should be actively treated.

Subjects can receive bisphosphonate for the treatment of bone metastases. If systemic or local analgesia is not effective in controlling painful lesions of bone metastases, a small area of palliative radiotherapy (the area of the radiotherapy must be $< 5\%$ of the bone marrow region, and the percent bone marrow content in human skeleton is shown in the figure of **Appendix VI**) is allowed.

Palliative treatment for lesions outside the lungs and liver is allowed during the study (when the treatment of the subjects is needed to improve symptoms upon the onset of PD), including the treatments for pleural effusion, ascites, pericardial effusion, and radiotherapy for brain lesions. During such treatment, the study drugs should be interrupted until the end of the recovery period of palliative treatment.

All concomitant treatments and medications used within 30 days prior to the first dose and during the study should be documented in the eCRF in strict accordance with the GCP regulations. Subjects will be closely monitored if adverse reactions occur, and active symptomatic treatment will be given if necessary. The drugs used will be documented and described in the CRFs. Once the study treatment is interrupted, only the concomitant medication and treatment used to solve new or unresolved treatment-related AEs will be recorded.

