5.3.6. Progression-free survival (PFS)

PFS is defined in Section 4.1.6.

According to population/cohort, the Kaplan-Meier method will be used to analyze the median PFS, the corresponding 95% CI will be calculated using the Brookmeyer-Crowley method, and the PFS plot will be drawn. The proportion of subjects with PFS greater than or equal to 6/9/12 months will also be analyzed. The Kaplan-Meier method will be used to analyze the 6-, 9-, and 12-month PFS rates, and the corresponding two-sided 95% CIs will be calculated (using the log(-log) transformation by normal approximation with back transformation).

The K-M curve of PFS of apatinib 250 mg + SHR1210 200 mg (Stage I) vs. apatinib 375 mg + SHR1210 200 mg will be plotted.

5.3.7. 12-month overall survival rate (12-OS%)

12-OS% is defined in Section 4.1.7.

The Kaplan-Meier method will be used to analyze the 12-OS% of each population/cohort, and the corresponding two-sided 95% CI will be calculated (using the log(-log) transformation by normal approximation with back transformation).

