5.3.8. Overall survival (OS)

OS is defined in Section 4.1.8.

The Kaplan-Meier method will be used to analyze the median overall survival of each population/cohort, its 95% CI will be calculated using the Brookmeyer-Crowley method, and the survival curve will be plotted. The proportion of subjects with OS greater than or equal to 12/18/24 months will also be analyzed. The Kaplan-Meier method will be used to analyze 12-, 18-, and 24-month overall survival rates and the corresponding two-sided 95% CIs will be calculated (using the log(-log) transformation by normal approximation with back transformation).

The K-M curve of OS of apatinib 250 mg + SHR1210 200 mg (Stage I) vs. apatinib 375 mg + SHR1210 200 mg will be plotted.

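### The adverse-event summary by apatinib dose sets a 250 mg column that mixes Stage I with all of Stage II beside a 375 mg column that is Stage I only, so stage is mixed with dose

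*SAP*

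**What the plan says.** SAP 5.4.3 first summarizes adverse events by population and cohort. It then adds a second summary by dose: "AEs will be summarized by group (apatinib 250 mg + SHR1210 200 mg, apatinib 375 mg + SHR1210 200 mg) using descriptive statistics". SAP 5.4 bases all safety analyses on the safety set, which SAP 5.1.1 defines as all enrolled subjects with at least one dose.

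SAP section 5 defines the 375 mg group narrowly: "Only subjects who receive apatinib 375 mg + SHR1210 200 mg in Stage I are included". It attaches the 250 mg label to Stage II as well: "Apatinib 250 mg + SHR1210 200 mg are used in both Cohorts 1 and 3 in Stage II", with matching statements for Cohorts 2 and 4.

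For the time-to-event curves by dose, the SAP restricts 250 mg to Stage I. Section 5.3.6 plans "The K-M curve of PFS of apatinib 250 mg + SHR1210 200 mg (Stage I) vs. apatinib 375 mg + SHR1210 200 mg", and section 5.3.8 plans "The K-M curve of OS of apatinib 250 mg + SHR1210 200 mg (Stage I) vs. apatinib 375 mg + SHR1210 200 mg".

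The stages differ by design. Protocol 5.1, criterion 4, reads "Stage I: Patients who have undergone the second-line and above chemotherapy" for the first stage. Cohorts 1 to 3 require a single prior platinum doublet, and Cohort 4 requires no prior systemic treatment. Under Protocol 6.6.2, the general principle for Stage I tolerability subjects is that "all other adverse reactions with no clinically significant toxicity occurring during the tolerability observation period (Cycle 1 of drug administration) will not be treated"; in other cases "the subjects should be given an optimal supportive care during the treatment". Under Protocol 6.3, PK-expansion subjects start apatinib on Day 22 of Cycle 1, yet SAP 4.2.1 counts events as treatment-emergent from the first study treatment.

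**The concern.** A table with one column per apatinib dose invites the reader to attribute differences between columns to dose. Here the columns also differ in stage, and stage brings different prior chemotherapy, a different approach to some Cycle 1 reactions, and a different mix of tolerability and PK-expansion subjects. The table has no stratification by stage.

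This matters because incidence and severity of adverse events is the Stage I primary endpoint (Protocol 2.2) and Protocol 13.4.4 calls for adverse events by dose group. The SAP 5.4.3 table is the only specified summary of overall adverse events by dose. The population summaries do not fill the gap, because SAP section 5 combines Stage I 250 mg subjects with Stage II cohorts according to driver-gene status.

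**Working it through.** **1. Who is in each column.**

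| | 250 mg column | 375 mg column |
|---|---|---|
| Stage | Stage I plus Cohorts 1-4 (no limit stated) | Stage I only |
| Prior chemotherapy | Second-line and above (Stage I); one platinum doublet (Cohorts 1-3); none (Cohort 4) | Second-line and above |
| Cycle 1 reactions | Mostly optimal supportive care | Restricted in tolerability subjects |
| Apatinib start | Mostly Day 1 | Day 22 in the PK-expansion part |

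**2. Stage II total.** The plan's figure reproduces. Cohort 1: 62/0.8 = 77.5, rounded up to 78; an exact binomial check at n = 62 (at least 16 responses, true ORR 30%) gives 80.3% power. Cohorts 2 and 3: an exact 90% interval at 30% has width 0.299 at n = 30, and 30/0.8 = 37.5 rounds up to 38 each. Cohort 4: 20. Sum: 78 + 38 + 38 + 20 = 174, all at 250 mg.

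**3. Stage I at 250 mg.** Protocol 3.1 plans 10-12 tolerability subjects and 10-12 further PK-expansion subjects in a dose group found tolerable, so 20-24. The same plan at 375 mg gives 20-24.

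**4. Stage II share of the 250 mg column.**
- 20 Stage I subjects: 174/(174 + 20) = 174/194 = 89.7%.
- 24 Stage I subjects: 174/(174 + 24) = 174/198 = 87.9%.
- Sensitivity with Stage II before dropout inflation (62 + 30 + 30 + 20 = 142): 142/162 = 87.7% and 142/166 = 85.5%.
- Share in the 375 mg column: 0%.

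**5. PK-expansion share.** At 375 mg: 10/20 to 12/24, about half. In the pooled 250 mg column: 10/194 = 5.2% to 12/198 = 6.1%.

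**6. What a stage difference would do.** Suppose dose has no effect. Let p1 be the event rate in Stage I, p2 the rate in Stage II, and w the Stage II share. The 375 mg column shows p1 and the 250 mg column shows w·p2 + (1 − w)·p1. The apparent difference (375 minus 250) is w·(p1 − p2). The gaps below are assumptions, because the documents give no event rates by stage; w runs from 0.879 to 0.897.

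| Assumed p1 − p2 | Apparent difference |
|---|---|
| +5 points | +4.4 to +4.5 |
| +10 points | +8.8 to +9.0 |
| +15 points | +13.2 to +13.5 |
| −10 points | −8.8 to −9.0 |

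Almost the whole stage gap passes into the apparent dose difference, in whichever direction it runs.

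**7. Precision after restriction.** Approximate 95% half-width for a risk difference at an assumed 50% event rate, 1.96·√[0.25·(1/n1 + 1/n2)]:
- Stage I only: 20 v 20 gives 0.31; 24 v 24 gives 0.28.
- Pooled 250 mg: 194 v 20 gives 0.23; 198 v 24 gives 0.21.

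**The case against.** The strongest reply has four parts.

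**The pooling is inferred.** SAP 5.4.3 names the groups by dose and never states that 250 mg covers both stages. That is true. The reading rests on the absent Stage I label, the safety set, and the use of the same label for Stage II in section 5. If Stage I was meant, the label still needs adding.

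**No comparison is planned.** SAP section 3 disclaims hypotheses and inference, and this table has no difference, interval or test. That stands: error rates are not affected. A side-by-side descriptive table can still be misread as a dose effect.

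**A like-for-like summary exists.** SAP 5.4.2 summarizes clinically significant toxicity by dose group in the DLT set, which is Stage I only and bears on the tolerability rule. The Stage II dose is already chosen, and the documents tie no decision to the adverse-event table. This limits the stakes, but that summary covers only clinically significant toxicity over four weeks.

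**The direction is unknown.** A reader might infer that untreated Cycle 1 reactions and heavier pretreatment make 375 mg look more toxic than it is. The documents do not support that. The Protocol 6.6.2 restriction covers Cycle 1 of tolerability subjects only, allows symptomatic treatment of hypertension, rash, diarrhea, nausea and vomiting, and calls for proactive management of clinically significant toxicity. PK expansion is planned in every tolerable dose group, and its apatinib-free first 21 days would tend to lower early toxicity mainly in the 375 mg column. Cohort 2 carriers of sensitive EGFR mutations or ALK fusions must also have failed a targeted inhibitor, so the lighter pretreatment in Stage II refers to chemotherapy. Time on treatment may also differ by stage. This part of the reply stands in full.

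**Conclusion.** The point holds as a matter of what the table can show. As written, the adverse-event summary by dose does not separate dose from stage: about 88-90% of the planned 250 mg column is Stage II against 0% of the 375 mg column, and PK-expansion subjects are about half of one column and 5-6% of the other. The SAP avoids this in its PFS and OS curves by dose but not here.

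It does not show that either dose looks worse than it should. The 9-point figure is an assumed 10-point stage gap multiplied by the Stage II share; it illustrates how the gap carries through and is not an estimate. The harm is to interpretation only.

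The conclusion assumes that the unlabelled 250 mg group covers both stages, that planned numbers are met, and that PK expansion took place at both doses; actual enrolment is not given. It supports an inexpensive improvement to the table and does not call the trial's conclusions into question.

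**What to change.** In SAP 5.4.3:

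1. Add a 250 mg column restricted to Stage I, labelled as in 5.3.6 and 5.3.8, and make it the comparator for 375 mg.
2. Identify tolerability and PK-expansion subjects in both dose groups, and flag PK-expansion events with onset before the first apatinib dose.
3. Keep the all-250 mg summary, which gives the larger safety profile, but label it as pooled across stages and not a dose comparison. It need not be removed from the table.

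The cost is one revised table shell using data already collected. The comparator falls to about 20-24 planned subjects, widening the half-width in the calculation above from 0.21-0.23 to 0.28-0.31; splitting by subject type leaves 10-12 per cell, suitable for description only.

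Two limits remain. Stage I dose groups are enrolled in sequence without randomization (Protocol 3.1 and 4.1), so the restricted contrast is not free of confounding. Protocol 3.1.3 and 6.4 describe apatinib dose reduction only for the 375 and 500 mg groups, so the dose-reduction row is not comparable between columns even after the change and should carry a footnote saying so.
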